Research Protocol

**Evaluation of Training Curriculum and Service of
Improving Access to Community Therapies**

[name]

[name]

Introduction

Prevalence of common mental disorders

Depression and anxiety disorders are widespread both globally and locally (Kessler et al., 2005). In 2015, the worldwide prevalence of depression stood at 4.4%, while anxiety had a prevalence rate of 3.6% (World Health Organization, 2017). In the context of Hong Kong, the prevalence of major depressive disorder (MDD) reached 2.9%, whereas the prevalence of generalized anxiety disorder (GAD) was 4.2% (Lam et al., 2015). Given the detrimental effects of mental disorders on an individual's quality of life and productivity (Alonso et al., 2004; Lim, Sanderson, & Andrews, 2000), the delivery of mental health services is of paramount importance.

The psychological treatment accessibility gap

Nonetheless, the availability of psychological interventions falls significantly short of the demand for such services. Among those with mental health issues in Hong Kong, less than 30% utilized mental health services (Lam et al., 2015). New patients typically face a waiting period of approximately one year before consulting with a psychiatrist. Furthermore, consultations with a clinical psychologist occur only once every two to six months. Extended waiting times and infrequent follow-ups may present barriers to the utilisation of mental health services.

In addition, an imbalanced distribution of mental health resources contributes to the gap in accessibility. A majority of resources are heavily concentrated within hospital-based mental health services. Consequently, individuals with severe mental disorders receive a greater share of resources from the healthcare system, while those with less severe symptoms have limited access to resources. Moreover, waiting times for mental health services are determined by the severity of symptoms. As a result, individuals experiencing mild to moderate depression or anxiety face longer waiting periods before their initial meeting with a mental health professional. In essence, those with less severe mental illnesses have access to fewer resources and experience longer waiting times, further diminishing their access to psychological treatments.

Improving Access to Psychological Therapies

In an effort to bridge the accessibility gap, the UK launched the Improving Access Psychological Therapies (IAPT) programme, aimed at individuals with mild to moderate depression and anxiety (Whiteford et al., 2013). The National Institute for Clinical Excellence (NICE) guidelines recommend cognitive behavioural therapy (CBT) as the primary treatment for those with lower severity mood disorders. Numerous studies have

consistently found evidence supporting the effectiveness of traditional, high-intensity, face-to-face CBT. Low-intensity cognitive behavioural therapy (LICBT), developed through the IAPT programme, has received empirical backing in the treatment of MDD, GAD, panic disorder, and specific phobia (Clark, 2011; NICE, 2004; NICE, 2009). The IAPT programme not only fosters early identification and categorisation of mental health issues but also enables efficient resource allocation based on severity. Individuals with less severe symptoms receive low-intensity interventions, while those with more severe psychiatric problems are escalated to intensive treatment.

Clark et al. (2009) showed that among participants who attended two or more sessions, 55-56% had recovered after the intervention's conclusion, with clinical outcomes maintained at a 10-month follow-up. Similarly, Richards and Suckling (2009) reported large pre-post-treatment effect sizes for depression and anxiety, specifically 1.41 and 1.39, respectively. The combined remission and recovery rates were also high for both depression (76%) and anxiety (74%). In another extensive study, 40.3% of participants achieved reliable recovery, and 63.7% demonstrated reliable improvement after receiving the IAPT programme (Gyani, Shafran, Layard, & Clark, 2013). Overall, numerous investigations have indicated that LICBT in the form of guided self-help successfully alleviates mild to moderate depressive and anxiety disorders. According to a meta-analysis conducted by Cuijpers, Donker, van Straten, Li, & Andersson (2010), the efficacy of guided self-help is comparable to that of traditional CBT in treating mood disorders (Cohen's $d = -0.02$). The benefits of the guided self-help approach include reduced waiting times for mental health services and the timely provision of interventions for mild to moderate mood disorders.

LICBT is a disorder-specific intervention, it adopts different CBT intervention strategies for different presenting problems, for example, behavioural activation for depression, worry time and problem solving for generalised anxiety, and exposure and habituation for panic and phobia. Transdiagnostic intervention has been gaining evidence over the past decade to target the underlying psychological mechanism and thus treat different presenting problems with the same set of strategies. Acceptance and commitment therapy (ACT) is one of the well-researched intervention approaches. Meta-analysis showed that ACT can effectively reduce the level of depression and anxiety, while brief ACT approach also showed promising results (Bai, Luo, Zhang, Wu, & Chi, 2020; Haller, Breilmann, Schröter, Dobos, & Cramer, 2021; Kyllönen, Muotka, Puolakanaho, Astikainen, Keinonen, & Lappalainen, 2018).

Mental Health in Hong Kong

Due to the huge success of the IAPT programme, its concept is worth borrowing and applying to Hong Kong. Mind Mental Health Hong Kong (Mind HK) has launched a programme named Improving Access to Community Therapies, or ‘iACT’ for short. iACT was developed in accordance with the IAPT programme and incorporated the principles of low-intensity psychological intervention and ACT principles. In this programme, Mind HK will train 30 bachelor’s degree holders to study a low-intensity psychological intervention programme. The study programme consists of 120 hours of intensive training and a 9-month placement in community settings, including non-government organisations, schools, and private clinics. The trained psychological well-being practitioners (PWPs) will provide low-intensity acceptance and commitment therapy (LIACT) to around 300 adults who are screened with mild to severe depressive or anxiety symptoms without imminent risk.

Individuals will later receive LIACT offered by PWPs and complete guided self-help workbooks with guidance. PWPs will be trained and supervised for providing LIACT. In addition to the 120-hour training, they received regular supervision from recognised supervisors, including clinical psychologists, social workers, and experienced counsellors. Aspects of case management and clinical skills will be covered during supervision. Despite the promising results of the IAPT programme, the effectiveness of LIACT in a local context has yet been examined.

Aims of the study

The current study aims to conduct a comprehensive evaluation of a training curriculum designed for teaching low-intensity psychological interventions to bachelor's degree holders, specifically focusing on principles of Acceptance and Commitment Therapy (ACT) and its intervention effectiveness. This evaluation is divided into two integral parts. In the first part, the curriculum, which encompasses a 120-hour intensive teaching block followed by a nine-month placement, will be evaluated. To assess the trainees' competencies in applying the principles of ACT, a series of role-play examinations will be administered at various time points, including pre-training, pre-placement, mid-placement, and end-of-placement. Focus groups will be conducted.

The second part of the evaluation is to examine the outcomes of low-intensity psychological interventions, delivered by the trainees, targeting adult individuals (age ≥ 18) screened with mild to severe symptoms of depression and anxiety. To achieve this, a series of questionnaires will be administered at several stages: pre-intervention, during each session, and at a three-month follow-up. Outcome measures will include the assessment of depressive

and anxiety symptom severity, quality of life, functional impairment, therapeutic alliance, and the level of experiential avoidance. Individual exit interviews and focus groups will be conducted.

Hypotheses

It is hypothesised that the competency level of the training participants will increase after the intensive training block and the placement. It is hypothesised that after receiving the low-intensity psychological intervention based on the Acceptance and Commitment Therapy (ACT) principle, the depression and anxiety scores, functioning impairment, and experiential avoidance level will reduce, and quality of life and therapeutic relationship will improve.

Methodology

Training Participants

Participants from the Psychological Wellbeing Practitioners (PWPs) Programme will be invited to participate in the research. The PWPs are degree holders who will undergo 120 hours of intensive training block, followed by 9 months of placement to practise the learnt skills. Given therapist competency will be part of the programme, this research will request the participants to consent to the use of the data collected in the programme.

Service Participants

Individuals with depression or anxiety symptoms will be sampled in this study. Participants will be recruited from the placement organisations and promotions on social media, web pages, and at mental health centres. The sample size is estimated to be 300 individuals for initial screening for LIACT-guided self-help services.

Inclusion criteria

1. Adults aged 18-65
2. Adults with a specific set of presenting problems
3. Anxiety problems (including social, generalised, health anxiety, work anxiety)
4. Mild to moderate depression
5. Other emotional challenges include (but not limited to): Low self-esteem, perfectionism, mild anger issues, interpersonal or relational challenges, low motivation, lack of purpose, and numbness

Exclusion criteria

1. Adults with the following features/presentations are not eligible for the PWP programme and should automatically lead to an onward referral:
2. High severity on depressive score (PHQ9 \geq 20)

3. High or imminent risk (according to scores on PHQ9 question no. 9 and information emerging at triage assessment, including indication of plan and action or the lack of protective factor)
4. Any of the following presentations or situations: diagnosis or features of a mental health problem that is not suitable for low-intensity intervention, obsessive compulsive disorder, post-traumatic stress disorder, bipolar disorder, schizophrenia and other psychotic disorders, dissociative disorders, personality disorders, eating disorders, gender dysphoria, paraphilic disorders, anger issues as primary presenting concern (without anxiety or depression), sleep issues as primary presenting concern (without anxiety or depression), psychotic experiences (e.g. hallucinations), substance-related disorders, history of trauma or abuse that is considered highly relevant to the current presenting problem they are seeking support for, planned changes to psychotropic medication during the period of PWP intervention, currently receiving regular psychological counselling or support from another practitioner for at least twice a month, diagnosis of a learning disability, cognitive impairment or neurodevelopmental condition that would impair their ability to engage with a structured, manualised intervention (e.g. untreated ADHD or moderate-severe brain injury), clear safeguarding concerns requiring multi-agency support (e.g. concerns about domestic abuse)

Research design

For training evaluation, given the current training programme has already consists of therapist competency assessment to ensure the quality of the training participants. A record of role-play videos will be rated the ACT therapist competency by trained psychologists at pre-training, after intensive training block, mid-placement and post-placement. A consent form will be sent to the training participant to authorise the use of data for analysis. Repeated measures design will be adopted for this study.

Repeated measures design will be adopted for this study. Individual guided self-help LIACT service, eligible participants will receive 6-8 sessions of guided self-help LIACT over three to four months. Clinical outcomes (depression and anxiety levels) will be measured at every session, it will take around 5 minutes to complete these two routine outcome measures. Other primary and secondary outcome measures, including general well-being, functioning and activity impairment, psychological flexibility, experiential avoidance, and therapeutic alliance will be at 3 time points, namely pre-treatment, post-treatment (at the end of the last session) and 6-week follow-up. Participants will take around 20 minutes to complete the full package of assessments. These outcome variables will be additionally measured after each

session to avoid missing data if participants drop out. Recovery rate and reliable improvement rate will also be used as indicators to evaluate the efficacy of LIACT. Focus groups will be conducted on participants who drop out and complete the programme to understand their experience and journey.

Curriculum

The LIACT training curriculum is designed by registered clinical psychologists with consultation from local ACT experts from the Association of Contextual and Behavioural Science (Hong Kong Chapter). There are 5 modules in the intensive training block including introduction, professional and ethics issues, application of ACT low-intensity intervention, troubleshooting and preparation for clinical placement. The LIACT protocol is also piloted and revised by clinical psychologists to ensure its adaptability to local situations. After 120 hours of intensive training, the training participants will attend a role-play exam to ensure their competency to proceed with the 9-month placement. During the 9-month placement, each PWP is expected to see at least 15 direct service beneficiaries to provide LIACT. During which, supervision will be provided regularly to ensure the quality of service delivery and risk management. There will be a mid-placement review and final placement review, and the training participants will submit audio recordings for supervisors to rate for their competence. Focus groups will be conducted for the training participants to understand their learning experience.

Treatment

Guided self-help LIACT will be provided to eligible participants. For individual guided self-help LIACT service, intake assessment will be conducted to assess the presenting problem of the participants at pre-treatment to ensure the suitability to receive LIACT service. Participants will be given the LIACT self-help workbook collaboratively with a PWP. Between each session, clients will read through the workbook and complete the exercises suggested in the workbook. In subsequent sessions, PWP will guide clients to overcome the difficulties in performing the LIACT exercises.

Therapists

PWPs will be responsible for providing LIACT to the participants. PWPs have completed a 120-hour intensive training and pass the role play examination prior to placement provision. The training was provided by experienced clinical psychologists and counsellors. Moreover, PWPs are under regular supervision by clinical psychologists, experienced counsellors, or social workers with extensive ACT training.

Outcome Measures

Training evaluation.

1. General counselling skills - ENhancing Assessment of Common Therapeutic factors rating scales (ENACT; Kohrt et. al., 2015): The 18-item ENACT scale assesses the levels of common factors in psychotherapeutic settings. The domains covered include *non-verbal and verbal communication, rapport and self-disclosure, collaborative processes, problem-solving, assessing functional impairment* etc. Each item is rated on a scale from 1 (“needs improvement”) to 3 (“done well”).
2. ACT competency - The ACT Fidelity Measure (ACT-FM; O’Neill et. al., 2019): ACT-FM is a 25-item measure evaluating the clinicians’ fidelity to ACT according to four key aspects: *Therapist Stance, Open Response Style, Aware Response Style and Engaged Response Style*. The measure focuses on the therapists’ frequency of desired and unpreferred therapeutic behaviour. It is possible for therapists to demonstrate both ACT-consistent (e.g. “Therapist helps the client to notice thoughts as separate experiences from the events they describe”) and -inconsistent (e.g. “*Therapist imposes their own, other’s or society’s values upon the client*”) behaviours to co-exist, therefore, the scores are calculated into two separate subscales - ACT Consistency Score and ACT Inconsistency Score, both range from 0 to 36 marks.

Service evaluation.

1. Depression level: The PHQ-9 (Patient Health Questionnaire-9) is a widely-used self-report screening tool designed to assess the severity of depressive symptoms in individuals. The PHQ-9 contains nine items, each corresponding to one of the major depressive disorder criteria. Respondents are asked to rate the frequency with which they have experienced each symptom over the past two weeks on a 4-point Likert scale, ranging from 0 (not at all) to 3 (nearly every day). The total score ranges from 0 to 27, with higher scores indicating greater severity of depressive symptoms.
2. Anxiety level: The GAD-7 (Generalised Anxiety Disorder-7) is a self-report questionnaire designed to assess the severity of generalised anxiety disorder symptoms in individuals. It comprises seven items, each reflecting a symptom of generalised anxiety disorder as outlined in the Diagnostic and Statistical Manual of Mental Disorders (DSM). Respondents are asked to rate the frequency with which they have experienced each symptom over the past two weeks on a 4-point Likert scale, ranging from 0 (not at all) to 3 (nearly every day). The total score ranges from 0 to 21, with higher scores indicating a greater severity of anxiety symptoms. The GAD-7 is widely used in clinical and research

settings for screening, diagnosis, and monitoring treatment outcomes in patients with anxiety disorders.

3. Well-being: The World Health Organisation - Five Well-Being Index (WHO-5) is a questionnaire that measures current mental well-being, originally developed to assess both positive and negative well-being. This five-question version uses only positively phrased questions to avoid symptom-related language. Response options are indicative of the frequency of particular feelings (e.g. "I woke up feeling fresh and rested.") in Likert format, ranging from 0 ("at no time") to 5 ("all of the time").
4. Functioning impairment: The Work and Social Adjustment Scale (WSAS; Mundt et. al., 2002) is a self-report measure developed to assess functional impairment in daily life across five domains: work, home management, social leisure, private leisure, and family relationships. Each domain is rated on a 9-point Likert scale, ranging from 0 (no impairment) to 8 (very severe impairment), with higher scores indicating greater functional impairment. The total score ranges from 0 to 40. The WSAS is commonly used to evaluate the impact of psychological disorders on an individual's daily functioning and to monitor treatment progress.
5. Psychological flexibility: The Acceptance and Action Questionnaire (AAQ-2; Bond et. al., 2011) is a widely-used measure designed to assess psychological inflexibility, which is a central concept in Acceptance and Commitment Therapy (ACT). In this 7-item self-report scale, participants choose from 1 ("never true") to 7 ("always true") to depict the relevance of the statements and themselves.
6. Therapeutic alliance: The Working Alliance Inventory (WAI) was developed by Horvath and Greenberg in 1989. The brief revised version (Brief Revised Working Alliance Inventory; BR-WAI) consists of 12 items available multilingually (including Chinese). The scale is rated on a 5-point Likert scale, ranging from 1 (never) to 5 (always).
7. Experiential avoidance: The Brief Experiential Avoidance Questionnaire (BEAQ; Gámez et. al., 2014) is a shortened 15-item self-report measure designed to assess experiential avoidance, or the avoidance of uncomfortable or distressing thoughts and emotions. These statements are scored on a scale ranging from 1 (strongly agree) to 6 (strongly disagree).
8. Work Productivity and Activity Impairment: Work Productivity and Activity Impairment Questionnaire: General Health (WPAI) was developed by Reilly et. al. (1993) to measure impairments in both paid work and daily activities due to health-related problems. The domains covered include work time missed, impairment at work, productivity loss and activity impairment.

9.

Data analyses

For individual service, only the data of participants who have attended two or more follow-up sessions will be included for analysis. The first assessment session will not be counted for this requirement. Firstly, inter-correlations among all outcome measures will be assessed with Pearson's correlation coefficients. Secondly, the changes in outcome variables between pre-treatment, post-treatment and 3-month follow-up will be evaluated with repeated measures ANOVA. Cohen's *d* will be calculated to assess the relative effect sizes. Furthermore, reliable significant improvement will be computed according to the method recommended by Jacobson & Truax (1991), which is the division of pre-post treatment score difference by the standard error.

Compliance

The protocol of this study complies with the Declaration of Helsinki, IGH-GCP and research ethics principles to protect the rights, safety and well-being of participants.

References

doi:10.1111/j.1600-0047.2004.00329.x

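### The pre-treatment BR-WAI score is not an interpretable alliance baseline, so the planned pre-post test mixes forming a therapeutic relationship with improving one

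*Combined protocol and SAP*

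**What the plan says.** The Hypotheses section predicts that, after the intervention, "quality of life and therapeutic relationship will improve". Research design puts alliance on the common schedule: "therapeutic alliance will be at 3 time points, namely pre-treatment, post-treatment (at the end of the last session) and 6-week follow-up". The Data analyses section then states that "the changes in outcome variables between pre-treatment, post-treatment and 3-month follow-up will be evaluated with repeated measures ANOVA", with Cohen's d as the effect size. It makes no exception for alliance and gives it no separate baseline. The design has one group and no comparator.

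The instrument, listed under Outcome Measures, is the 12-item BR-WAI, with each item rated from 1 (never) to 5 (always).

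The only pre-treatment contact described is in the Treatment section: "intake assessment will be conducted to assess the presenting problem of the participants at pre-treatment to ensure the suitability to receive LIACT service". The protocol does not say who conducts this intake, or whether the forms are completed before or after it.

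Research design adds that these outcome variables are measured again after each "session to avoid missing data if participants drop out". The Data analyses section does not use those scores as an alliance baseline.

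**The concern.** A client has a level of depression, functional impairment or avoidance before treatment starts, so a pre-treatment score on those scales has a plain meaning. A working alliance exists only once client and practitioner are working together. Before that, a frequency-type item can be answered literally (never), from expectation, at mid-scale or not at all. After an intake with the eventual practitioner it can be answered from one non-treatment contact. The protocol does not say which of these the baseline represents.

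The planned contrast starts from that score. If the ANOVA shows a rise, the reader cannot tell whether alliance grew during LIACT or whether a relationship simply came into being. If it shows no rise, the reader cannot tell whether alliance was flat or the baseline was inflated by hope. With no comparator, nothing in the design separates these explanations. The hypothesis on the therapeutic relationship therefore has no clean test, and its Cohen's d has no clear meaning.

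**Working it through.** The protocol gives no expected alliance score, SD, alpha or power, so there is no figure to reproduce. The check is a decomposition with stated assumptions.

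**1. What the planned contrast measures.** Let Pre be the pre-treatment score, S1 the score after the first treatment session and Post the score at the last session.

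Post − Pre = (Post − S1) + (S1 − Pre)

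The first term is growth in alliance during treatment, which is what improvement should mean. The second is the step from no relationship, or one intake contact, to a first rating of a real one. The ANOVA tests the sum.

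**2. Possible size of the second term.** From the protocol: 12 items rated 1 to 5, so the total, if items are summed, runs from 12 × 1 = 12 to 12 × 5 = 60. Assumed: a rating of 4 per item at S1 and at Post (12 × 4 = 48), so Post − S1 = 0. With an assumed baseline of b per item, the artefact is 48 − 12b.

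| Assumed baseline per item | Pre total | Apparent change with no growth after session 1 |
|---|---|---|
| 1 | 12 | +36 |
| 2 | 24 | +24 |
| 3 | 36 | +12 |
| 4 | 48 | 0 |
| 5 | 60 | −12 |

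The protocol gives no basis for choosing a row.

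**3. Sensitivity of the test, if a shortfall exists.** Use a normal approximation to a paired test at an assumed two-sided alpha of 0.05, with Post − S1 = 0. The probability of declaring improvement is Φ(dz√n − 1.96), where dz is the baseline shortfall divided by the SD of the paired difference. Both n and dz are assumed; the only sample figure in the protocol is 300 people for initial screening.

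| n | dz = 0.2 | dz = 0.3 |
|---|---|---|
| 100 | 0.52 | 0.85 |
| 150 | 0.69 | 0.96 |
| 300 | 0.93 | >0.99 |

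In points: a shortfall of 0.25 per item is 12 × 0.25 = 3. With an assumed SD of 10, dz = 3/10 = 0.30. At n = 150, 0.30 × √150 − 1.96 = 1.71, and Φ(1.71) = 0.96. These probabilities are conditional on a shortfall; they do not show that there is one. The test is two-sided, so a baseline inflated by the same amount gives the same probability of a significant fall.

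**4. After the change.** With S1 as baseline the second term drops out. If alliance is flat after session 1, the expected change is 0 and the false-positive rate is the nominal one (0.05 as assumed). Power for a true increase cannot be computed, because no SD or expected change is given.

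**The case against.** A reader might infer that the hypothesised improvement is largely built in, or that the hypothesis could hardly fail. The protocol does not support that. Such a conclusion needs a baseline near the floor, and nothing in the text says how clients answer before treatment. They may answer mid-scale or hopefully, which would shrink, remove or reverse the artefact. They may also leave items blank, which would cost cases in the ANOVA.

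The baseline may also follow real contact. The Data analyses section distinguishes an opening assessment session from the sessions that come after it, which is compatible with one practitioner doing both. If the form is completed after intake with that practitioner, the planned baseline is only one contact earlier than the one proposed here. This softens the problem without removing it: an intake is a check of presenting problem and suitability, and the text does not confirm that the practitioner is the same.

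Two further objections stand. A follow-up rating of a relationship that has ended is retrospective, but that does not make it invalid, and excluding it from inference would be a preference. The claim that no new data are needed also depends on the after-each-session measurements including the BR-WAI. That is the natural reading of Research design, but it is not stated explicitly.

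**Conclusion.** The point holds as one about interpretability. The planned baseline precedes treatment or follows at most one intake contact, and change from it confounds forming an alliance with improving one. The direction and size of the bias are unknown. Under the assumptions shown, the artefact runs from 36 points down to 0 on a scale spanning 48 (12 to 60), and turns negative if clients rate hopefully. The conclusion does not depend on any row of that table, because the baseline lacks a clear meaning in every case.

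The scope is one of several hypothesised outcomes. The symptom and functioning scales, and the recovery and reliable-improvement rates, are unaffected. The change is nonetheless worth making, because a named hypothesis cannot be interpreted as written and the remedy costs almost nothing.

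**What to change.** For BR-WAI only:

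- In Research design, define the baseline as the rating after the first treatment session, and confirm that the after-each-session measurements include the BR-WAI.
- In Data analyses, test change from that rating to the last session attended, and leave the pre-treatment BR-WAI score out of that test. Report any follow-up rating as retrospective.
- In Hypotheses, state that alliance will increase from the first to the last treatment session.
- If a pre-treatment BR-WAI is still collected, state who conducts intake and when the form is completed.

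The cost is a few lines of text and, if the after-each-session forms include the BR-WAI, no new data. The reported alliance gain will probably be smaller. With a single group, the result will describe growth during treatment and will not establish its cause.

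Separately, the follow-up is at 6 weeks in Research design but at three months in Aims of the study and Data analyses. These statements must be reconciled.

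### Does the undefined recovery rate, with an analysis set that ignores entry scores, distort the reported recovery and reliable improvement rates?

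*Combined protocol and SAP*

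**What the plan says.** The Research design section introduces two responder rates: "Recovery rate and reliable improvement rate will also be used as indicators to evaluate the efficacy of LIACT". Data analyses does not mention recovery again. It describes reliable improvement by the Jacobson-Truax method, "which is the division of pre-post treatment score difference by the standard error", from pre- to post-treatment. Its one analysis set for the individual service is based on attendance: "only the data of participants who have attended two or more follow-up sessions will be included for analysis", with the first assessment session not counted.

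Entry is bounded above but not below. The exclusion list has "High severity on depressive score", set at a PHQ-9 of 20 or more. No minimum PHQ-9 or GAD-7 is listed, and the inclusion list also has "Other emotional challenges include (but not limited to): Low self-esteem, perfectionism, mild anger issues". Elsewhere the population is described as symptomatic. Service Participants says "Individuals with depression or anxiety symptoms will be sampled in this study", and the section on mental health in Hong Kong says "screened with mild to severe depressive or anxiety symptoms without imminent risk". Neither statement has a score attached.

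The background section on the UK programme cites a recovery figure over a similar attendance set: "among participants who attended two or more sessions, 55-56% had recovered after the" intervention ended. It does not define recovery.

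**The concern.** Both scales stop at 0, so nobody can fall by more than their entry score, and nobody below a cut-off can move from case to non-case. If reliable change takes 6 points, PHQ-9 entry scores of 0 to 5 can never qualify. That is 6 of the 20 admissible values (0 to 19). Someone eligible because of anxiety, perfectionism or low self-esteem may well score that low on PHQ-9.

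If these people stay in the denominator as failures, both rates depend on who was admitted as well as on what the treatment did. There is no control group to absorb this, and readers are likely to set the results beside the recovery (55-56%) and reliable improvement (63.7%) figures quoted in the background. A recovery definition settled after the scores are seen could also move the reported figure by tens of points.

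**Working it through.** The plan gives no planned recovery or improvement rate and no baseline distribution, so it has no figure to reproduce. The inputs below are assumptions, except for the scale limits and the PHQ-9 exclusion, which come from the protocol.

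**Inputs.** PHQ-9 at entry: mean 8, 10 or 12, SD 5, scores rounded and limited to 0-27, entries of 20 or more removed. Mean fall 4 points, pre-post correlation 0.5, reliability 0.85.

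**Required change.** 1.96 × SD × √(2(1 − reliability)) = 1.96 × 5 × √0.30 = 5.37, so a whole-point fall of 6. At reliabilities 0.80 and 0.90 the threshold is 6.20 and 4.38, so 7 and 5 points.

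**The dilution argument.** In any one dataset, rate over all = (1 − f) × rate among those able to qualify, where f is the share entering too low. Holding the second factor at 42.6% gives 0.426 × 0.9 = 38.3% at f = 10% and 0.426 × 0.7 = 29.8% at f = 30%. That looks like an 8-point swing with the same benefit.

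**Does the second factor stay fixed?** Simulated PHQ-9 reliable improvement at a 6-point threshold:

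| Entry mean | Enter too low | Rate over all analysed | Rate among those able |
|---|---|---|---|
| 8 | 31% | 32.6% | 47.4% |
| 10 | 19% | 34.5% | 42.6% |
| 12 | 10% | 34.4% | 38.4% |

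It does not. Between the first and last rows the share entering too low differs by 21 points. The rate over all differs by 34.4 − 32.6 = 1.8 points, and the restricted rate by 47.4 − 38.4 = 9.0. With a lower entry mean, those at 6 or above are a more selected group and regress further towards the mean, which inflates their apparent improvement. The pattern repeats at reliability 0.80 (over all 25.2, 27.0, 27.0%; restricted 41.0, 36.0, 31.6%) and at 0.90 (40.7, 42.6, 42.5%; restricted 53.9, 49.5, 45.7%). A rerun with a different random seed agreed with these figures to within 0.3 points.

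**Recovery.** With an assumed PHQ-9 cut-off of 10 and entry means 8, 10 and 12:

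- Case to non-case, over all analysed: 28.5, 34.8, 37.1%.
- Case to non-case, over baseline cases: 75.7, 66.2, 55.4%.
- Ending below the cut-off, over all analysed: 65-87%, highest at mean 8.

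At mean 8, relative to the rate over baseline cases, low entrants pull the result down by 75.7 − 28.5 = 47 points on the first reading and up by about 87 − 76 = 11 on the third. The attendance rule does not choose between these readings. It says whose data enter the analysis, and sets no numerator or denominator for recovery.

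**The case for a change.** The strongest counter-argument is that recovery really is undefined. With no comparator, a figure that could land anywhere from 28% to 87% depending on unwritten choices and the entry mean is weak evidence, and a few sentences would settle it at no cost in data. The gap is real, and nothing elsewhere in the documents closes it. The time point is open too, because Research design gives a 6-week follow-up while Aims and Data analyses give three months.

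The dilution identity also stands as arithmetic. If low scorers arrive as a separate stream, for example through the other emotional challenges route, and everyone else is unchanged, the rate over all does fall by the factor (1 − f). The table above instead shifts the whole entry distribution. The documents do not show which picture is closer.

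Neither point carries the concern through. People who enter low are not excluded, but nothing shows how many there will be. The symptomatic-population wording and the intake suitability assessment both point to fewer. With an assumed floor of 5 on either scale, and improvement on either scale counting, the gap between the two denominators is only 0-6 points.

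**Conclusion.** The concern does not call for a change.

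**Recovery** is a missing definition, not a wrong rule. In ordinary use the word implies starting as a case, so an analyst would naturally take it over participants at or above the chosen cut-off at pre-treatment. Depression and anxiety are scored at every session, so whichever scale and cut-off are used, the rate and the number starting below it can be computed and reported. A downward bias is not established, since the direction depends on the reading.

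**Reliable improvement** has a stated method and a pre-post interval. Reporting it over everyone analysed is a fair description of what the service achieved. Restricting it by entry score is a debatable trade-off: in an uncontrolled study it selects for regression to the mean, and in the model the restricted rate was the more sensitive to case mix (9 points against under 2).

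**Consequence.** Both rates are supporting indicators. The service hypotheses concern levels of symptoms, impairment, avoidance, quality of life and therapeutic relationship; these are examined by repeated measures ANOVA with Cohen's d, which none of this touches.

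Apart from the floor arithmetic (an entry score below 6 cannot fall by 6), every figure rests on the assumed means, SD, reliability, correlation, fall and cut-off. The residual risk is that the recovery definition is chosen after the scores are seen. A reader should therefore look for the stated definition and denominator before giving weight to a reported recovery rate.
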